3.11.3 MCP-Mod/Non-standardized sigmoidal Emax model

This analysis will be performed using the R software (DoseFinding package) using MCPMod a wrapper function that calls MCTtest, which performs this multiple comparison test of differences based on the multivariate T-statistic.

MCP-Mod methodology: [Bretz, et al \(2005\)](#).

3.11.4 LOG-RANK

The survival distribution for time to the first fall will be estimated for each treatment group (bimagrumab 700 mg, bimagrumab 210 mg and bimagrumab 70 mg, placebo). Each of the bimagrumab treatment groups will be compared to the placebo treatment group using a log-rank test. The SAS[®] procedure LIFETEST including covariates, if relevant, will be used as follows:

```
proc lifetest data=... OUTSURV =...
conftype = linear method = KM alpha = 0.05 alphaqt = 0.05 plots = (SURVIVAL
(FAILURE NOCENSOR )) ;
    time fall1*status(1);
    strata region [REDACTED] frfix histfall mobaid vitd / group = trtn;
```

run;

where fall1 = time to first overall fall from Day 1

trtn = treatment group

region = region (Japan/Non-Japan)

[REDACTED]

frfix = fracture fixation type (internal [screws only, intramedullary {nails} and extramedullary fixation {plate, combinations}]/arthroplasty [hemiarthroplasty or total hip arthroplasty])

histfall = history of falls (yes/no [none])

mobaid = use of mobility aids prior to hip fracture (yes/no [none])

vitd = 25OH vitamin D at Screening (< 30 nmol/L [<12 ng/mL] / ≥ 30 nmol/L [<12 ng/mL])

status (1) = indicates an event of first fall

If a patient does not have a fall event the data will be censored at the time of study completion, premature discontinuation or if ongoing in the study at the last available assessment date, 1 indicating censored variables.

Time to first cardiac safety event will be analyzed in a similar manner, where time to fall will be replaced with time to the start of the first cardiac event as identified by the adjudication committee.

Time to first orthopedic event will be analyzed in a similar manner, where time to fall will be replaced with time to the start of the first orthopedic event as identified by the adjudication committee.

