5.3 Treatment assignment, randomization

At the randomization visit, all eligible patients will be randomized via Interactive Response Technology (IRT) to one of the four treatment arms. The investigator or his/her delegate will contact the IRT after confirming that the patient fulfills all the inclusion/exclusion criteria. The IRT will assign a randomization number to the patient, which will be used to link the patient to a treatment arm and will specify a unique medication number for the first package of investigational treatment to be dispensed to the patient. The randomization number will not be communicated to the caller.

The randomization numbers will be generated using the following procedure to ensure that treatment assignment is unbiased and concealed from patients and investigator staff. A patient randomization list will be produced by the IRT provider using a validated system that automates the random assignment of patient numbers to randomization numbers. These randomization numbers are linked to the different treatment arms, which in turn are linked to medication numbers. A separate medication list will be produced by or under the responsibility of Novartis Drug Supply Management using a validated system that automates the random assignment of medication numbers to packs containing the investigational drugs.

Randomization will be stratified using the following three strata: 1) Japanese sites, 2) Non-Japanese sites for patients randomized 21 days or less from their hip fracture surgery date, and 3) Non-Japanese sites for patients randomized greater than 21 days from their hip fracture surgery date. This measure will balance the distribution of Japanese patients among bimagrumab treatment groups and the placebo group. Therefore it will support the analysis of comparison of key efficacy and safety endpoints for Japanese sub-population.

The randomization scheme for patients will be reviewed and approved by a member of the Randomization Group. A separate randomization list was already created at the time of amendment 2.

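### SAP 3.11.4 codes the first-fall status variable both ways, and its log-rank code crosses at least five factors with no rule for choosing them

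*SAP*

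**What the plan says.** SAP 3.11.4 (LOG-RANK) compares each bimagrumab group with placebo on time to first fall, using PROC LIFETEST. Two features of the section matter here.

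- **Status code.** The TIME statement puts 1 in the parentheses after the status variable. The variable list below the code says "status (1) = indicates an event of first fall". The next paragraph, on patients without a fall, ends "1 indicating censored variables".
- **Strata.** The STRATA statement lists region, one redacted item and then "frfix histfall mobaid vitd / group = trtn". The visible variables are defined with two levels each: "region = region (Japan/Non-Japan"), "frfix = fracture fixation type (internal" or arthroplasty), "histfall = history of falls (yes/no [none"]), "mobaid = use of mobility aids prior to hip fracture (yes/no [none"]), and vitamin D split at 30 nmol/L. The lead-in says covariates are included if relevant and does not say how relevance is decided.

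The section then applies the same method to time to first cardiac event and time to first orthopedic event.

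Elsewhere, Protocol 5.3 states "Randomization will be stratified using the following three strata": Japanese sites, non-Japanese sites with randomisation 21 days or less after surgery, and non-Japanese sites with randomisation later than that. The negative binomial model for falls (SAP 3.11.9) adjusts only for treatment date and region. Protocol 9.5.1.3 makes the log-rank test optional and conditional on enough events.

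**The concern.** The two status definitions cannot both hold. A programmer who derives the variable from the list and runs the code as printed gets an inverted analysis, and the template passes the same ambiguity to two safety outputs.

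The stratification is a separate matter. With treatment named in the GROUP option, the variables in STRATA define cells, and treatment arms are compared only within a cell. A fall that occurs when only one arm is still at risk in its cell adds nothing to the test. With many cells and few falls, information is lost for no stated benefit. Because relevance has no rule, the set of factors could also be settled after the treatment codes are known.

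**Working it through.** **1. Status code.** Three statements are to be compared. The TIME statement makes 1 the censoring value, because PROC LIFETEST reads the parenthesised value that way. The censoring paragraph agrees. The variable list says the opposite. If the data followed the variable list, then in a 70 versus 70 comparison with about 22 first falls (step 4), those 22 patients would be treated as censored and 140 − 22 = 118 patients without a fall as events.

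**2. Number of cells.** Five visible binary factors give 2^5 = 32 possible cells. Randomisation has 3. Average patients per arm per cell: 70/32 = 2.2 for the 210 mg, 700 mg and placebo groups, and 35/32 = 1.1 for the 70 mg group (group sizes from SAP 2.13).

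**3. The SAP's own falls figures.** The documents state no power or event count for the log-rank test. The only falls calculation is SAP Table 2.6: negative binomial, 140 versus 70 patients, k = 1, 9 months, two-sided 0.05. With n0 = 70, θ = 2 and t = 0.75,

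V = (1/t)(1/r0 + 1/(θ·r1)) + (1 + θ)k/θ, and power = Φ(√n0·|ln(r1/r0)|/√V − 1.96).

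For 0.10 versus 0.30: V = (1/0.75)(3.33 + 5) + 1.5 = 12.61, and power = Φ(8.367 × 1.0986/3.551 − 1.96) = 73.5%. The five rows come out at 16.6, 43.6, 73.5, 19.8 and 52.8%, against 16.3, 42.9, 72.7, 19.5 and 52.0% in the table. All agree within one point, so the inputs are read correctly.

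**4. Expected first falls.** P(at least one fall) = 1 − (1 + k·r·t)^(−1/k), with k = 1 and t = 0.75, times 70 per arm.

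- 0.30: 0.1837 × 70 = 12.9. 0.21: 0.1361 × 70 = 9.5. Total 22.4.
- 0.30 versus 0.10: 12.9 + 4.9 = 17.7.
- 0.40 versus 0.20: 16.2 + 9.1 = 25.3.

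The largest of the five table rows, 0.40 versus 0.28, gives 16.2 + 12.1 = 28.3. All are below 32.

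**5. Cost of the stratification.** Simulated stratified log-rank test: 70 versus 70, gamma frailty with k = 1, 9 months, 2000 runs, factors unrelated to falls. Prevalences are an assumption, because the documents give none. Each cell shows all factors at 50%, then factors at 15–50%.

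| Falls per year, active vs placebo | Power, 3 strata | Power, 32 cells | First falls that contribute, 32 cells |
|---|---|---|---|
| 0.21 vs 0.30 | 11.4 / 10.6% | 9.5 / 10.2% | 87 / 90% |
| 0.10 vs 0.30 | 53.2 / 53.2% | 42.8 / 45.6% | 88 / 90% |
| 0.20 vs 0.40 | 34.2 / 33.2% | 27.0 / 29.2% | 87 / 89% |

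With three strata all first falls contribute. Repeat simulations at the same rates widen the ranges: 10–17% of first falls contribute nothing; power with 32 cells is 40–47% at 0.10 versus 0.30; and power goes from 31–36% to 25–29% at 0.20 versus 0.40.

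**6. A higher fall rate.** Protocol 6.4.5 mentions 40–60% of patients falling again within a year. Assuming half of the placebo patients fall by 9 months (1.333 per year, halved on active) gives about 58 first falls. Power goes from about 55% with three strata to 41–47% with 32 cells, and 82–88% of falls contribute. The loss is of similar size.

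**The case against.** **The full crossing may not be intended.** The code is introduced with the qualifier about relevance, and Table 2.2 lists falls as a by-group presentation for the same visible factors. A template run one factor at a time is plausible. No visible body section of the SAP describes the time-to-first-fall analysis, so such text may be redacted. This stands as a limit: 32 is what the printed code produces, not a proven intention. It leaves the reader without a rule either way.

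**The status slip would be caught.** The executable line and the later sentence agree, inverted curves would show most patients falling, and the SAP version history records dry-run reviews of outputs. That makes it a wording error rather than a flaw of method, but it is still a wrong definition in the governing text.

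**Little depends on this test.** At the SAP's own meaningful ratio of 0.7 the log-rank test has about 11% power with three strata, so it says little under any scheme. This stands.

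**Stratifying on prognostic factors is legitimate.** It is, and neutral factors give that approach no credit. It does not justify cells averaging two patients per arm.

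Several stronger readings are tempting, but the documents do not support them.

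- *Sixty-four strata.* This needs the redacted slot to be a single binary factor, which cannot be verified.
- *Treatment date has been left out.* It could be the redacted item. Either way the strata are not the three used at randomisation.
- *Cardiac and orthopedic tests will be run on a handful of events.* SAP 2.11.6 runs the cardiac analysis only if at least 10% of patients have an event, and treats orthopedic events similarly. In 140 patients that is at least 14 events, which is few for 32 cells but not a handful.
- *The confirmatory falls claim is at risk.* The fifth inference in SAP 2.10.2.3 uses the negative binomial model.

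**Conclusion.** The status contradiction is certain from the text and would reverse the event and censoring roles if the wrong definition were programmed. The stratification point holds for the code as printed: 32 possible cells, of which fewer may be populated, for about 18 to 25 first falls in the scenarios simulated. Power falls by about 6 to 13 points at 0.10 versus 0.30 per year, subject to the assumed prevalences and to factors unrelated to falls.

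The harm is lost information and an undefined choice, not false positives: in a null simulation with about 14 events the error rate stayed near 5%. The log-rank test is supportive, so neither the gated falls inference nor the trial's type I error control changes. The point should be corrected before programming, but it does not threaten the main conclusions.

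**What to change.** - Delete "status (1) = indicates an event of first fall" and state once that 0 = fall (event) and 1 = censored, for the falls, cardiac and orthopedic analyses alike.
- Replace the STRATA list with the three randomisation strata (Japan; non-Japan, 21 days or less; non-Japan, more than 21 days) and remove the qualifier about relevance.
- If adjustment for fixation type, fall history, mobility aids or vitamin D is wanted, put it in an optional supportive Cox model.

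The cost is one definition and one line of code, with no new data. The small downside is that the log-rank test itself no longer adjusts for the other prognostic factors.

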Amended to explain the rationale for the change in cardiac safety monitoring introduced in this amendment and that the independent adjudication of image-based fracture healing complications will be performed by the central image reader only.

[REDACTED]

[REDACTED]

[REDACTED]

Section 7.2.1: SAE reporting

Amended to clarify that all X-ray based findings pertinent to delayed fracture healing (i.e. bone non-union at W36/W48) will have to be reported as SAE.

Section 8.4: DMC

Text has been updated to indicate that the DMC will review unblinded data outputs following recent changes in Guidelines to DMC activities.

Section 8.5: Adjudication

This section has been updated to reflect that an independent adjudication committee to reassess and confirm pre-specified AEs/SAEs reported by investigators will be utilized for cardiovascular events only. The scope of adjudication which includes ischemic heart disease,

[REDACTED]

heart failure, cardiomyopathy, and certain cardiac arrhythmias, was clarified. The section also highlights that independent adjudication of image-based fracture healing complications will be done by the central image reader only.

Section 9: Data Analysis

Amended to highlight that the primary analysis (summary of W24 data) is planned to be supplemented by additional analysis of all efficacy data available at the time of the primary analysis to obtain preliminary insight into the robustness/durability of potential therapeutic effects

Section 9.1.1: Study medication

This section was amended to correct the calculation of exposure to last infusion date minus first infusion date plus 56 days (instead of 28 days).

Section 9.5.2.2: Bone Safety Analysis

Amended to reflect current focus of interest concerning orthopedic complication (fracture healing complications with focus on incidence of delayed bone-union).

[REDACTED]

[REDACTED]

Section 12: References

[figure not shown]
Updated by references used in the current amendment

[REDACTED]

[figure not shown]
[figure not shown]
[REDACTED]

[figure not shown]
[figure not shown]
Amendment 2

[figure not shown]
[figure not shown]
Amendment rationale

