The risk to patients in this trial will be minimized by compliance with the eligibility criteria, close clinical monitoring and guidance for the investigators provided in the Investigator's Brochure. An adjudication committee will review cardiovascular events to confirm that these events have been evaluated appropriately and diagnosed correctly, while a Data Monitoring Committee (DMC) will monitor safety data from the study and the entire bimagrumab program for potential safety concerns.

As for any other investigational drug, there are unknown risks to bimagrumab, which may be serious and unforeseen.

Benefits

The benefits of bimagrumab treatment in the hip fracture population are still not known. However, it is expected that as seen in healthy volunteers and patients with sIBM, the hip fracture patients will have an increase in muscle mass that may translate to better recovery of lower extremity function and faster return to mobility. Over the course of the study, the number of falls might be reduced, which in turn reduces the risk of traumatic injuries and fractures, including secondary hip fractures.

4 Population

The study population will consist of male and female patients ≥ 60 years old, at time of randomization, who underwent surgical treatment for a low-energy fracture of the proximal femur. The study aims to screen approximately 400 patients. With an estimated screen failure rate of about 40%, approximately 245 patients, with successful surgery after hip fracture, will be randomized in more than 60 centers worldwide. Approximately 200 patients are expected to complete the 24-week treatment epoch and approximately 120 patients the full 48 -week study period.

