6.5.7 X-ray assessment of surgical procedure

A historical X-ray done by local practice during or after surgery (in some cases prior to the initiation of screening) will be used by the investigator for eligibility assessment. The summary of the local assessment will be recorded in the Perioperative eCRF and must confirm adequate surgical execution of internal fixation or arthroplasty for fracture repair. Images do not need to be submitted to the central reader vendor.

During the trial, an X-ray of the operated hip will be taken at Week 24 (EoT) visit - as indicated in [Table 6-1](#) - to assess whether fracture healing has been completed (bone union) and whether there are any potential late complications of the surgery. If bone-union is not achieved at Week 24, patient will be followed up at Week 36 and also potentially at Week 48 (EoS), if bone union is still not achieved at Week 36. Additional unscheduled X-rays may also be required if there is any clinical suspicion of delayed/improper fracture healing. Any findings on X-ray need to be reported as adverse events. Specifically, bone non-union seen at Week 36 (delayed fracture healing) needs to be reported as an SAE.

All scheduled and unscheduled X-rays performed after enrollment will be transferred to a central reader (details provided in *Imaging Manual*). Two independent readers of the assigned

vendor will perform a blinded assessment of the images for bone union and a number of pre-specified orthopedic complications. In case of discordant medical opinions regarding the presence or absence of these complications, a third reader will settle a final decision. The central reader may request sites to provide additional X-rays, if available, to support overall assessment of the specific finding.

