8.5 Adjudication Committee

An independent cardiovascular adjudication committee will be used to re-evaluate and confirm the investigator-reported diagnostic term of specific safety events (e.g. ischemic heart disease, heart failure, cardiomyopathy, or cardiac arrhythmias). Events will be reviewed blindly as they occur during the trial. Details regarding the adjudication process will be available in the relevant Adjudication Committee charter. The committee may provide expert reports at the end of the study.

The clinical database will be regularly searched by the clinical team for targeted adverse events including but potentially not limited to cardiac safety events. When an adverse event in these categories is identified, a follow-up form will be sent to the clinical site to document the adverse event in detail and to request the submission of any applicable supplemental data, which may be available, including copies of source documents. Source documents include, but are not limited to, relevant clinical notes, radiographs, ECGs, ultra-sonograms, operative and pathology reports, hospital discharge summaries. In addition, an interview with the patient conducted by the site (in person or via telephone) may be needed to fully clarify the circumstances of the event.

The outcome of the adjudication or the expert review will be captured in the clinical data base.

[figure not shown]
9 Data analysis

The primary analysis for this study will be conducted when all patients have completed the (double-blind) treatment epoch (Week 24 visit). All post-treatment follow-up data on efficacy endpoints (SPPB and gait speed) available at the time of the primary analysis will also be summarized to address the durability of functional benefits during the off-drug follow-up period. The final statistical analysis will be performed when all patients have completed Week 48 of the study.

All details regarding the statistical analysis will be documented in the statistical analysis plan which will be finalized prior to the data extraction for the primary analysis (Week 24) at interim database lock and the global study team group level unblinding.

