In addition, provided again that there are a sufficient number of events ($\geq 10\%$ of patients have at least one event), the time to the first cardiac event over the course of the study (as calculated relative to the start of first infusion of study drug) will be estimated for each treatment group and “Active Total: Safety”. Kaplan-Meier estimates for median time to first cardiac event with 95% confidence interval, 25th and 75th percentiles will be presented. Patients not experiencing a cardiac event will be censored at the time of study completion, premature discontinuation or if ongoing in the study at the last available assessment date. The survival distributions of time to first cardiac event will be compared between each active bimagrumab treatment group, “Active Total: Safety” and placebo by means of the log-rank statistic (see [Section 3.11](#) [Statistical methodology and assumptions]).

As the number of cardiac rhythm disturbance, heart failure, ischemic heart disease and cardiomyopathy events are expected to be low, descriptive statistics (see [Section 3.2](#) [Precision and summary statistics]), will be performed on the questions listed in the Cardiac rhythm disturbances, Heart failure, Ischemic heart disease and Cardiomyopathy eCRFs. Any information recorded in the Adverse events eCRF for an AE which is deemed to have an AE classification of “Cardiac rhythm disturbances”, “Heart failure”, “Ischemic heart failure” or “Cardiomyopathy” will also be summarized descriptively, if relevant.

Orthopedic events

Orthopedic events (i.e. fracture healing complications) will be summarized in a similar manner as the cardiac safety events described above. These events are expected to be rare and orthopedic information is recorded in the Orthopedic complications eCRF.

Hospitalizations

Hospitalizations will be summarized in a similar manner as the orthopedic/cardiac safety events described above. Descriptive statistics (see [Section 3.2](#) [Precision and summary statistics]) will be presented for certain characteristics as recorded in the Hospitalization eCRF. These are:

- Number of patients hospitalized and number of hospitalization events (E).

- Reasons for hospitalization:
 - Injurious fall with fracture.
 - Other.
- Place of discharge:
 - Home.
 - Long-term care facility.
- Average duration of hospitalizations (days) = Duration of hospitalization (Date of discharge – date of admission) / Number of hospitalizations.

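### SAP 3.11.4 names the wrong event source for the conditional time-to-first-orthopedic-event analysis: a committee that the protocol describes as cardiovascular

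*SAP*

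**What the plan says.** SAP 3.11.4 sets out the log-rank method for time to first fall and then extends it to cardiac and orthopedic events in two parallel sentences. The orthopedic one takes "time to the start of the first orthopedic event as identified by the adjudication committee".

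SAP 2.11.6 adds: "Orthopedic events (i.e. fracture healing complications) will be summarized in a similar manner as the cardiac safety events described above". It goes on to say that these events are expected to be rare and that the information sits in the Orthopedic complications eCRF. In the cardiac text that it points back to, the odds ratio rests on committee-confirmed events, and the time-to-event analysis runs only if at least 10% of patients have an event.

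On the committee, protocol 8.5 says: "An independent cardiovascular adjudication committee will be used to re-evaluate and confirm the investigator-reported diagnostic term of specific safety events". The examples that follow are all cardiac. Protocol 3.6 agrees: "An adjudication committee will review cardiovascular events to confirm that these events have been evaluated appropriately and diagnosed correctly".

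On fracture healing, protocol 6.5.7 has two independent readers at the imaging vendor; the "vendor will perform a blinded assessment of the images for bone union and a number of pre-specified orthopedic complications". If they disagree, "a third reader will settle a final decision". Protocol 6.5.12 also names two independent central readers for this task.

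**The concern.** The orthopedic sentence in SAP 3.11.4 looks like the cardiac sentence with one word changed. It makes an orthopedic event count only if a committee has identified it, and nothing in the protocol gives the committee that task. An analysis programmed as written would find no qualifying events, and the result could be reported as too few events when the cause is the definition.

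Orthopedic complications are part of a secondary safety objective (protocol 2.2). Protocol 6.5.12 explains the X-ray monitoring by the first use of the drug in patients after major hip-fracture surgery, and 7.2.1 treats non-union at Week 36 or later as serious. The preclinical signal should not be overstated: 6.5.12 reports slight callus changes in skeletally immature rats only, with no difference in radiographic healing or biomechanics.

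A programmer who noticed the problem would have to choose between central readings and investigator eCRF entries without a pre-specified rule. That choice might come after the biostatistics team has been unblinded at patient level for the primary analysis (SAP 2.4.1).

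**Working it through.** The documents give no power, event count or alpha allocation for this analysis, so there is no stated figure to reproduce. The check compares the texts, with one line of arithmetic.

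**1. Who identifies the event**

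| Place | Event source |
|---|---|
| SAP 3.11.4, orthopedic time to event | Adjudication committee |
| SAP 2.11.6, orthopedic paragraph | Orthopedic complications eCRF, handled like the cardiac events |
| Protocol 3.6 and 8.5 | Committee described as cardiovascular |
| Protocol 6.5.7 and 6.5.12 | Central X-ray readers for union and complications |
| Protocol 9.5.2.2, bone safety | X-ray imaging; no committee |
| SAP 3.11.8, orthopedic odds ratio | Flag for at least one event; no committee |

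SAP 3.11.4 is the only place that explicitly assigns orthopedic events to the committee. Protocol 9.5.2.1 bases the cardiac relative risk on confirmed events, while 9.5.2.2 puts no such condition on bone safety, so the protocol keeps the two apart. SAP 2.14, which lists departures from the protocol, records no new orthopedic adjudication.

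**2. Literal consequence.** Orthopedic events identified by a cardiovascular committee: 0. If the cardiac 10% condition carries over, the number of patients needed is 0.10 × 245 = 24.5, that is 25. Zero is below 25, so the analysis would not be run. If the condition does not carry over, the analysis would be run with no events.

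**3. Does the rule spread to the odds ratio?** The cardiac odds ratio in SAP 2.11.6 uses committee-confirmed events.
- If handling orthopedic events similarly includes that condition, the orthopedic odds ratio loses its events too, in conflict with protocol 9.5.2.2 and SAP 3.11.8.
- If it covers only the layout and methods, the odds ratio is intact.

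The text allows both readings.

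**4. What does not depend on the committee.** These are the incidence and treatment contrasts in protocol 9.5.2.2, the bone-fracture-healing query in SAP 2.11.6, the X-ray findings in SAP 2.11.11 (summarized if numbers suffice, always listed), and the odds ratio as SAP 3.11.8 states it.

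**The case against.** The strongest reply is that little is lost. The time-to-event analysis is supportive and conditional, orthopedic events are expected to be rare, and 25 patients with an event may never be reached under any definition. Fracture healing is also covered by the X-ray, query-based and AE/SAE outputs and by the external DMC. This stands, and it limits the size of the point.

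A second reply is that the committee's remit is not closed. Protocol 8.5 gives its event types as examples, speaks of "targeted adverse events including but potentially not limited to cardiac safety events", lists radiographs among the source documents, and leaves details to a charter that is not available here. This stands in part: current 8.5 does not say that the committee reviews cardiovascular events and nothing else. But the phrase describes the clinical team's database search, no text gives the committee an orthopedic task, and 6.5.7 assigns the X-ray decisions elsewhere. The Amendment 3 log, as background, agrees: "independent adjudication of image-based fracture healing complications will be done by the central image reader only".

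A reader might infer that the whole fracture-healing evaluation has no events. The documents do not support that, because the analyses in step 4 of the working keep their own sources and the events are still collected. Nor is it established that the orthopedic odds ratio is lost; that follows from only one reading of SAP 2.11.6.

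**Conclusion.** The point holds for one analysis. SAP 3.11.4 assigns the time-to-first-orthopedic-event analysis to a source that, on the protocol's description, does not produce orthopedic events. Followed literally, it yields zero qualifying events, and the analysis is either empty or not run. The orthopedic odds ratio in SAP 2.11.6 is exposed only through the ambiguity about similar handling.

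This rests on two assumptions: that the unseen charter gives the committee no orthopedic remit, and, for the figure of 25 patients, that the 10% condition carries over and about 245 patients are treated. The primary and secondary efficacy analyses are untouched. The defect is worth correcting because it concerns a named safety topic and could pass unnoticed as sparse data.

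**What to change.** In SAP 3.11.4:
- Replace the committee, for orthopedic events, with a named source. Central-reader-confirmed findings should be the main one, in line with protocol 6.5.7 and 9.5.2.2. Report Orthopedic complications eCRF events separately or under a stated precedence rule.
- State which date counts as onset. X-rays are scheduled at Week 24 and, if union is incomplete, at Weeks 36 and 48, so a radiographic finding is dated by when it was looked for unless another rule is given.
- Settle the status coding before the code is reused: the section describes the value 1 both as a first fall and as censored.

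In SAP 2.11.6:
- Say that committee confirmation applies to cardiac events only.
- Say whether the 10% condition applies to orthopedic events.

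The cost is a few sentences of SAP text. The readings and eCRF entries are already being collected. The change should be made before the treatment codes are released to the analysis team.
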